6.0 STUDY TREATMENTS

6.1 Investigational Products and Controls

Absorica® (isotretinoin) will be provided in a capsule form for oral consumption. The capsules should be swallowed whole. In this study, Absorica® will be taken twice daily for a total daily dose of approximately 1 mg/kg/day, to attain a target cumulative dose of 120 to 150 mg/kg during the active 20-week course of therapy.

During the first 4 weeks of the treatment period, subjects will receive doses of 0.5 mg/kg/day divided into 2 daily doses of 0.25 mg/kg. During the remaining 16 weeks of the study, subjects will receive approximately 1 mg/kg/day divided into 2 daily doses of approximately 0.5 mg/kg/day. The subject will be instructed to take each dose without food, specifically, at least 2 hours after the previous meal or at least 1 hour before the next meal.

The dose will be delivered as 10 mg, 20 mg, 25 mg, 30 mg, 35 mg, or 40 mg capsules, with the number of capsules dependent upon the body mass of the subject as shown in [Table 6-1](#). To decrease the risk of esophageal irritation, subjects will be instructed to swallow the capsules with a full glass of liquid.

[figure not shown]
[figure not shown]
6.2 Dosing Justification and Regimen

The dosage range recommended in the Absorica® (isotretinoin) package insert is 0.5 mg/kg/day to 1 mg/kg/day given in 2 divided doses without regard to meals for 15 to 20 weeks.

[figure not shown]
The dosing regimen selected for this study is consistent with approved labeling for isotretinoin in both the US and Canada. The overall goal is to standardize the dosing and assure a uniform cumulative drug exposure in order to uniformly assess any emergent adverse events (AEs), yet to remain within the dosages approved in the labeling.

In trials comparing 0.1, 0.5, and 1 mg/kg/day, it was found that all dosages provided initial clearing of disease, but that retreatment was more likely to be necessary if lower dosages were used. Therefore subjects will be titrated up to a maximum dose of 1 mg/kg. Higher dosages (ie,

2 mg/kg/day) are recommended only in adults with particularly recalcitrant acne and should not be given in this study.

6.3 Packaging and Labeling

Study medication will be stored in a locked cabinet at the study site in accordance with the site procedures for storage of investigational products. Study medication should be stored at controlled room temperature (68°F to 77°F or 20°C to 25°C) with excursions permitted to 59°F to 86°F (15°C to 30°C).

Subjects who qualify for study entry will receive a 30-day supply of study medication at each visit during the ATP beginning at Baseline (Visit 2).

6.4 Assignment to Treatment

6.4.1 Randomization

Not applicable. All subjects will receive treatment according to the same regimen. There will be no randomization or stratification.

6.4.2 Blinding

Not applicable. This is an open-label study.

6.5 Prior and Concomitant Therapy

All medications, including OTC drugs, taken within 30 days prior to the start of the study will be recorded at Screening. Thereafter, a record of all medications and supportive therapy taken during the course of the study will be made. Information regarding the total daily dose, route of administration, start and discontinuation dates, and indication are to be recorded on the subject's eCRF.

Restricted or prohibited medications and treatments are listed in the Exclusion Criteria ([Section 5.3.5](#)).

6.6 Contraception

Female subjects of childbearing potential must follow the iPLEDGE requirements regarding contraception. Both a primary and a secondary form must be used while in the ATP phase of the study.

Primary forms	Secondary forms

• Tubal sterilization• Partner's vasectomy• Intrauterine device• Hormonal (combination oral contraceptives, transdermal patch, injectables, implantables, or vaginal ring)	
Barrier forms (always used with spermicide)
 
• Diaphragm• Cervical cap 
Barrier forms (used with or without spermicide)
 
• Male latex condom 
Others:
 
• Vaginal sponge (contains spermicide)

Unacceptable Forms of Contraception include:

- Progesterone-only “mini-pills,” eg:
 - Ortho Micronor® Tablets
- IUD Progesterone T
- Female condoms
- Natural family planning (rhythm method) or breastfeeding
- Fertility awareness
- Withdrawal
- Cervical shield* (* A cervical shield should not be confused with a cervical cap, which is an effective secondary form of contraception. See page 20 of iPLEDGE).

Some medications used concomitantly with hormonal contraceptives may decrease the effectiveness of the birth control products. The study investigators are advised to EXERCISE CAUTION and consult the package insert of the medications prior to administering them to females of childbearing ability. Drugs that are known to decrease the effectiveness of hormonal contraceptives should not be used concomitantly with the study medication.

6.7 Allowed Medications

The following medications, preparations, and treatments are acceptable to use during the study:

- Simple analgesics or cold preparations (ie, Tylenol) taken for headache, cough and/or common cold, etc;
- Low dose inhaled corticosteroids;
- Lip balms, skin moisturizers and mild skin cleansers, nasal lubricant gel, natural tears;
- Medicines prescribed under a doctor's care that are taken on a regular basis for at least 3 months and at doses that have not changed more than 25% in the last 60 days, unless disallowed in the study protocol;
- Medications that are prescribed by primary care providers to the subject during the course of the trial. If the subject is prescribed a medication for a medical condition during the trial, the investigator is to evaluate the medication and medical condition to ensure the subject can safely continue to participate in the trial.

6.8 Disallowed Medications

Subjects who had used the following medications at any time are to be excluded from the study:

- Tegison® (etretinate).

- Soriatane® (acitretin).

Use of the following medications, preparations, and treatments is disallowed as noted below.

- 30 days prior to Baseline and throughout the study (both ATP and PTP):
 - Systemic corticosteroids.
 - Spironolactone and its derivatives.
- 14 days prior to Baseline and throughout the study:
 - Antibiotics. Tetracyclines are prohibited during the study. Short courses of other antibiotics can be administered during the study at the discretion of the investigator. [Note: Per [Section 5.3.5](#), antibiotics and tetracyclines are prohibited during ATP but allowed during the PTP]
 - Phenytoin (eg, Dilantin);
 - Any other medication used to treat acne (both ATP and PTP).
- 7 days prior to Baseline:
 - Topical corticosteroids.
- During the study (both ATP and PTP):
 - Vitamin A supplements > 1000 µg for males and >800 µg for females (ATP and PTP)
 - Herbal products (St. John's Wort, red clover, milk thistle, etc).
 - Microdose progesterone preparations (see [Section 6.6](#)).
 - Oral contraceptives with approved anti-acne indication for nodular acne (eg, Ortho Tri-Cyclen®, Yaz®, and Estrostep®). Females using oral contraceptives with anti-acne activity are allowed to continue using them if they had been on the contraceptive for at least the last 3 months prior to screening and there was no improvement in the status of their acne. For subjects who remain on an oral contraceptive during the PTP, it is preferred that they continue on the same medication as in the ATP; if any change is required, it is preferred that the medications named above be avoided. All medications taken should be documented.

6.9 Adherence to Dosing Regimen

Records of study product used and dosages administered will be kept during the study. Subjects will be issued a diary in which they are to record the date and time they take each dose of study medication. Subjects will be instructed to bring the diary, all unused study medication, and all packaging from used study medication to each post-Baseline study visit in the ATP. Use of study drug will be reconciled, and the number of missed doses as noted in the diary will be recorded.

Subjects who are consistently noncompliant (ie, <75% of required doses) will be counseled and may be withdrawn from the study.

After reconciliation of study medication use, all study medication packaging and unused study medication will be returned to the subject.

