Isotretinoin (13-cis-retinoic acid) is an oral retinoid that has been approved in the US since 1982 for patients with recalcitrant, severe nodular or scarring acne, acne conglobata, and acne fulminans.⁵ Isotretinoin has also been used off-label as an effective treatment of acne that is either treatment-resistant or is producing physical or psychological scarring. Isotretinoin is the only agent that targets all pathophysiological processes of acne; it reduces the secretion of sebum, decreases the size of the sebaceous glands, prevents the development of comedones, and decreases the colonization with *Propionibacterium acnes* (*P. acnes*), the prevalent bacterium in acne. It also possesses anti-inflammatory properties, and reduces the levels of metalloproteinases in sebum.^{3,5} The approved dosage of 0.5 to 1.0 mg/kg/day⁶ is typically given over a 20-week course, to a total cumulative dose of 120 to 150 mg/kg.^{4,5,7} Beyond this maximal dosing, no further benefit has been reported. However, if this dosage range has not been achieved, patients

are more likely to relapse and require subsequent courses of therapy.⁵ Patients often require only a single course of treatment with isotretinoin and improvement continues even after the drug has been stopped.³

In one study, 69% of patients (61/88) were still virtually clear of disease an average of 9 years after completing treatment with isotretinoin, whereas of the remaining patients, 16% required further treatment with conventional antibiotics and 23% required a second course of isotretinoin.⁸ Relapses have been reported to occur in approximately 23% of patients (primarily during the first 2 years after treatment discontinuation) even in patients who received a full course of 150 mg/kg of isotretinoin.⁹ Recent studies examining risk factors for relapse in patients treated with isotretinoin emphasize the importance of the total cumulative dose rather than the daily dose used during treatment. Patients treated with a lower cumulative dose (less than 120 mg/kg) have a significantly higher recurrence rate than patients treated with a higher cumulative dose.⁴ One study found a significant association between acne relapse and the following factors: male gender, age under 16 years, living in an urban area, isotretinoin cumulative doses above 2,450 mg, and isotretinoin treatment longer than 121 days.¹⁰

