5.0 SELECTION OF STUDY POPULATION

5.1 Subject Population

It is planned to enroll approximately 200 subjects at approximately 20 sites in the US in order to provide approximately 140 subjects who complete the ATP. An individual subject will be allowed to participate in the study one time only. A rationale for the choice of sample size is provided in [Section 8.2](#) of this protocol.

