5.4 Discontinuation of Treatment

In accordance with legal requirements and International Conference on Harmonization (ICH) – Good Clinical Practice (GCP) guidelines, every subject has the right to refuse further participation in this study at any time and without providing reasons. A subject's participation is to be terminated immediately upon his/her request. The Investigator should seek to obtain the reason and record this on the electronic case report form (eCRF), whenever possible.

If, at the time of refusal, a study product has already been administered, the subject should be advised on follow-up safety investigations.

In the case of significant disease or intolerance of study medication, the decision to stop treatment for a given subject can be made by the investigator alone. If such a treatment discontinuation occurs, the investigator will notify the sponsor and provide medical justification.

A subject may be withdrawn from the study at any time at the discretion of the investigator for medical reasons and/or due to non-adherence to the treatment scheme and other duties stipulated in the study protocol. The reasons for early termination are to be fully documented on the eCRF.

In addition, the sponsor reserves the right to end or suspend the study at any time (see [Section 9.2](#)).

If a subject withdraws from the study, all efforts will be made to complete the final evaluation procedures at the time of termination if possible. Protocol-specified withdrawal procedures are the same as those to be performed at the End of Treatment (EOT) visit (if withdrawal occurs during the ATP) or at the End of Study (EOS) visit (if withdrawal occurs during the PTP).

Subjects discontinued for an AE will be monitored until the AE is resolved, a reasonable explanation is provided for the event, or the subject is referred to his/her own primary medical doctor. The specific AE in question will be recorded on the appropriate CRF.

Subjects who prematurely discontinue the study will not be replaced.

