7.4.5 Pregnancy Testing

Female subjects of childbearing potential will undergo a pregnancy test (urine or serum) at Visit 1 (Screening) before any study-specific procedures are performed. If the pregnancy test is positive, the subject will not be permitted to enroll in the study. Female subjects who test negative for pregnancy must use two approved methods of contraception for a mandatory one-month waiting period. These subjects must have a second pregnancy test conducted at least 19 days after the initial pregnancy test; and, if enrolled into the ATP, throughout the ATP and for 1 month after their last dose as specified in iPLEDGE.

Should a subject become pregnant during the study, treatment must be discontinued. Subjects should continue with non-treatment and/or follow-up visits.

All pregnancies should be immediately reported to the medical monitor and followed through to resolution (ie, delivery, miscarriage, or abortion). The report should be submitted within the same timelines as an SAE (within 24 hours of knowledge), although a pregnancy per se is not considered an SAE.

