8.2 Sample Size and Power Considerations

The sample size of 200 subjects was selected to provide adequate estimates of probable events in the population. Estimates of the endpoints of interest will be calculated with 95% 2-sided confidence intervals wherever possible. No statistical hypothesis tests are planned.

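### Follow-up after stopping study drug depends on the reason for stopping, and no text carries subjects who stop during the ATP into the 2-year retreatment follow-up

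*Combined protocol and SAP*

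**What the plan says.** What follows a stop of study drug is set out in four places:

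- **Non-adherence.** Section 6.9: "Subjects who are consistently noncompliant (ie, <75% of required doses) will be counseled and may be withdrawn from the study". Section 5.4 adds: "A subject may be withdrawn from the study at any time at the discretion of the investigator for medical reasons and/or due to non-adherence".
- **Adverse event, disease or intolerance.** Under 5.4 a subject discontinued for an AE is monitored until the event resolves, is explained, or the subject is referred to a personal physician. The investigator may also stop treatment for disease or intolerance. No further study visits are stated in either case.
- **Pregnancy.** Under 7.4.5 treatment stops and "Subjects should continue with non-treatment and/or follow-up visits".
- **Withdrawal during the ATP.** Sections 5.4 and 7.2.8 call for one return visit with the EOT procedures, including acne-QOL, lesion count and IGA. Nothing later is described.

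On numbers, Section 5.1 says "It is planned to enroll approximately 200 subjects at approximately 20 sites in the US", and gives the purpose as "in order to provide approximately 140 subjects who complete the ATP". Section 5.4 adds: "Subjects who prematurely discontinue the study will not be replaced". Section 8.2 justifies the size only in general terms: "The sample size of 200 subjects was selected to provide adequate estimates of probable events in the population". It plans 95% intervals and no tests.

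The PTP primary endpoints (4.2.2.1) are the proportion needing oral isotretinoin again and the time at which it is needed. They carry no completion or adherence condition. The ATP primary endpoint (4.2.1.1, 8.6) is expressly limited to completers who are at least 75% adherent.

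**The concern.** Stopping the drug and leaving the study are different events, and the second should not follow from the first unless the subject wants it to. Here a subject who takes too little drug can be taken out of the study altogether. One who stops for an AE has no stated place in the PTP. A pregnant subject who stops drug keeps attending. About 20 sites would have to decide for themselves what happens to the rest.

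At stake is the main long-term result of the study. If subjects who stop early are not asked about retreatment, the 2-year proportion describes a group selected partly on how much drug they took. Section 2.1 ties relapse to that factor ("Patients treated with a lower cumulative dose (less than 120 mg/kg) have a significantly higher recurrence rate"), and Section 6.2 says retreatment was more often needed at lower dosages. A confidence interval computed on those who remain will not reveal this selection, and no analysis can restore outcomes that were never collected.

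**Working it through.** **1. The plan's own figures.** Section 5.1 gives about 200 enrolled and about 140 ATP completers.

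- Implied non-completers: 200 − 140 = 60, and 60/200 = 30%.
- Inflating back: 140/(1 − 0.30) = 200. This shows only that the two figures agree, because the 30% is derived from them. No dropout rate, precision target or formula is stated.
- The 60 covers every cause, including voluntary withdrawal, and is counted among subjects enrolled. It is not broken down by reason.

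**2. Do stoppers differ in dose received?** The nominal schedule (4.1, 6.1) is 0.5 mg/kg/day for 4 weeks, then about 1 mg/kg/day for 16 weeks.

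- Full adherence: 0.5 × 28 + 1.0 × 112 = 126 mg/kg.
- 75% adherence: 0.75 × 126 = 94.5 mg/kg.
- Adherence needed for 120 mg/kg: 120/126 = 95%.
- Time needed for 120 mg/kg at full adherence: 28 + (120 − 14)/1.0 = 134 days, about Week 19.

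So subjects below 75% overall, and nearly all who stop early, fall short of 120 mg/kg. Retained subjects between 75% and 95% fall short too. The two groups differ in dose, but 120 mg/kg does not divide them cleanly.

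**3. Which way would the difference push?** Section 2.1 points both ways. It reports more recurrence below 120 mg/kg. It also cites a study associating relapse with cumulative doses above 2,450 mg and treatment longer than 121 days. At the minimum entry weight of 40 kg (5.2.2), a full course is 126 × 40 = 5,040 mg over 140 days, so full-course completers would all lie on the higher-relapse side in that study. The direction cannot be settled from the protocol.

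**4. What missing outcomes could do.** Assume 23% retreatment among those observed. That figure is borrowed from the background in 2.1. There it is a relapse rate, and separately a second-course rate in a study averaging 9 years of follow-up. It is not a planning value for 2-year retreatment. With x retreated among those observed and m unobserved, the proportion among 200 lies between x/200 and (x + m)/200.

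| Unobserved m | Observed x/n | Lowest | Highest |
|---|---|---|---|
| 60 | 32/140 | 16.0% | 46.0% |
| 30 | 39/170 | 19.5% | 34.5% |
| 10 | 44/190 | 22.0% | 27.0% |

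At an assumed 15% with m = 60 (21/140 observed), the range is 10.5% to 40.5%.

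**5. Precision, for comparison.** The 95% half-width is 1.96 × √(p(1 − p)/n).

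- p = 0.23, n = 140: 7.0 points.
- p = 0.23, n = 200: 5.8 points.

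Losing all 60 costs little precision. What it leaves open is who the estimate describes.

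**The case against.** The strongest reply is that the protocol is silent here and prescribes no exclusion. Nothing bars a subject who stops drug in the ATP from entering the PTP. Withdrawal for non-adherence is permissive, follows counselling, and its reasons must be documented. Section 5.4 does give stopping treatment and withdrawing from the study separate paragraphs. All of this stands, so the loss is possible and is not specified.

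A completer population is also a coherent reading of retreatment. Section 2.2 speaks of the period after treatment has been completed, 4.1 of a second course, and 5.1 states the enrolment target through completers. Someone who stops in Week 3 and later restarts may be finishing a first course. The ITT set in 8.3 is introduced for efficacy and is not assigned to the retreatment endpoint. Section 8.1 leaves detail to a SAP, and only the summary in Section 8 is available here. This has weight and is a reason to report completers separately. It does not remove the point: the sponsor wrote a completer condition into the ATP endpoint and none into the PTP endpoint, and a later SAP can choose an analysis set but cannot supply uncollected outcomes.

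A reader might also infer three stronger things that the documents do not support:

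- **That AE stoppers are followed for the AE and nothing else.** This comes from silence, and such a subject who withdraws should also have the EOT-type visit.
- **That about 60 of 200 dosed subjects will be lost.** The 200 are enrolled, and the 60 is an all-cause ceiling that includes people no rule could retain.
- **That discretionary withdrawal lets sites remove likely failures.** ATP withdrawal comes before any retreatment outcome, and nothing in the text suggests this use.

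**Conclusion.** The point holds as a gap in follow-up. Stated follow-up differs by reason for stopping, ATP withdrawal ends with one visit, and no text carries ATP stoppers into the PTP. Up to about 60 of about 200 enrolled subjects could therefore have no 2-year retreatment outcome, under an endpoint that is not restricted to completers. Those missing would differ in dose received, which the protocol links to relapse.

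Direction and size of the bias are unknown. The range of 16% to 46% is a worst-case bound that assumes 23% among 140 observed and all 60 others unobserved. It narrows to 22% to 27% if only 10 are unobserved. Further loss during the PTP is not counted, because the protocol gives no figure for it.

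A reader might infer that a completer-based figure would be about 8 points too low. That needs an assumed 50% rate in all 60 non-completers: (0.23 × 140 + 0.50 × 60)/200 = 31.1%, against 23%. The 50% has no basis in the documents, and equal rates would give no bias at all. The matter deserves correction before outcomes are lost, but it does not undermine the study as a whole.

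**What to change.** Reconcile 5.4, 6.9, 7.2.8 and 7.4.5 so that stopping study drug is recorded separately from withdrawing consent for follow-up. When and why drug is stopped, and the investigator's medical discretion, stay as they are.

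For subjects who stop drug and still consent to contact, record oral isotretinoin retreatment (yes or no, with date) through the 2-year period. Do this at PTP visits if they attend, and otherwise by a brief call to the subject or prescriber. Section 7.2.7 already uses such contact when a subject with a flare will not return. Count time from last dose. Since 20 + 104 = 124 weeks, the existing calendar already reaches 2 years after last dose for anyone who stops before Week 20.

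Report the proportion retreated and the time to retreatment for all treated subjects, and separately for ATP completers. State the number with unknown outcome and how they are censored.

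The cost is protocol and consent wording, plus a few short calls for at most about 60 subjects already enrolled. If all 60 chose to attend all six PTP visits, that would be 60 × 6 = 360 visits, and the telephone route keeps the burden well below this. Subjects who refuse all contact will still be missing.

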7.2.3 Active Treatment Period – Visit 3 (Week 2 ± 4 days)

- Reconcile the medication use and record the number of missed doses as indicated in the diary
- Review any concomitant medication used since the previous study visit.
- Review laboratory test results from the Visit 2 assessment.
- Query the subject regarding consumption of food around the time of dosing.

- Obtain blood samples for a laboratory profile including fasting clinical chemistry, and a fasting lipid profile.
- Perform a serum pregnancy test for females of childbearing potential. Ensure that female subjects of childbearing potential are following the iPLEDGE requirements.
- Record any AEs.
- Schedule the next study visit. Remind subject not to eat prior to the visit and to bring any unused capsules and used capsule packaging with them to the visit.

7.2.4 Active Treatment Period – Visits 4, 5, 6, and 7 (Weeks 4, 8, 12, and 16 ± 4 days)

- Reconcile the medication use and record the number of missed doses per the diary.
- Review any concomitant medication used since the previous study visit.
- Query the subject regarding consumption of food around the time of dosing and remind subject that dosing should be at least one hour before a meal or at least two hours after a meal.
- Obtain blood samples for a laboratory profile including fasting clinical chemistry and a fasting lipid profile.
- Perform a serum pregnancy test for females of childbearing potential. Ensure that female subjects of childbearing potential are using 2 approved method(s) of contraception.
- Have the subject complete the acne-QOL questionnaire.
- Complete the lesion count and IGA.
- Record any AEs.
- Obtain photographs of the subject's face.
- Prescribe a 30-day supply of study medication.
- Schedule the next study visit. Remind subject not to eat prior to the visit and to bring any unused capsules and used capsule packaging with them to the visit.

7.2.5 Active Treatment Period – Visit 8/End of Treatment Visit (Week 20 ± 4 days)

- Reconcile the medication use and record the number of missed doses per the diary.
- Review any concomitant medication used since the previous study visit.
- Query the subject regarding consumption of food around the time of dosing.
- Measure vital signs (systolic and diastolic blood pressure, heart rate, and respiratory rate) with subject in a seated position and record weight.
- Obtain blood samples for a laboratory profile including fasting clinical chemistry, and a fasting lipid profile.

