7.2.8 Early Termination

If a subject withdraws from the study during the ATP and prior to Week 20/Visit 8, the subject is to return to the site. All EOT procedures should be performed, including the administration of

the acne-QOL questionnaire, the lesion count, the IGA, and a pregnancy test (if applicable). The photography should be performed using the method assigned to the site.

If a subject withdraws from the study during the PTP and prior to Visit 14, the subject is to return to the site for an early termination visit. All EOS procedures should be performed, including the acne QOL, lesion count, the IGA, and photography. Subjects who require an additional course of isotretinoin therapy are to be discontinued after the EOS procedures are performed.

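### Section 6.9 returns all unused isotretinoin to the subject after reconciliation and makes no exception for Visit 8 or early termination, when treatment is over

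*Combined protocol and SAP*

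**What the plan says.** Section 6.9 (Adherence to Dosing Regimen) instructs subjects "to bring the diary, all unused study medication, and all packaging from used study medication to each post-Baseline study visit in the ATP". Use is then reconciled and missed doses are recorded from the diary. The section ends: "After reconciliation of study medication use, all study medication packaging and unused study medication will be returned to the subject". It attaches no condition to that sentence.

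Visit 8 is a post-Baseline ATP visit. Section 7.2.5 lists this step for it: "Reconcile the medication use and record the number of missed doses per the diary". Table 1-1 also marks reconciliation at Visit 8. Neither lists collecting capsules.

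For withdrawal, Section 5.4 says: "Protocol-specified withdrawal procedures are the same as those to be performed at the End of Treatment (EOT) visit", where withdrawal falls in the ATP. Section 7.2.8 repeats this and adds no drug-retrieval step.

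For pregnancy, Section 7.4.5 says: "Should a subject become pregnant during the study, treatment must be discontinued". It continues: "Subjects should continue with non-treatment and/or follow-up visits". It does not mention remaining capsules. The same section requires pregnancy testing "throughout the ATP and for 1 month after their last dose as specified in iPLEDGE".

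**The concern.** Handing capsules back between visits is sensible while dosing continues. Once treatment has ended there is no reason to do so, and Section 2.3 describes isotretinoin as a known teratogen with a birth-defect risk of about 30%.

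The protocol's reproductive safeguards are timed from the last dose: contraception for 1 month after stopping (Section 5.2.1, item 4) and pregnancy testing for the same period (Section 7.4.5). If a subject reported using leftovers, both would be extended. But the last scheduled pregnancy test is at Visit 9 (Section 7.4.4), no step after Visit 8 counts capsules, and the later visits only review reported medication (Sections 7.2.6 and 7.2.7). Undisclosed use would not be picked up by these steps.

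The reproductive risk concerns females of childbearing potential. The point is one of drug accountability and safety; it changes no endpoint, analysis population or estimate.

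**Working it through.** **Is there an exception elsewhere?**

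- Section 6.3 covers storage and dispensing only.
- Section 10.1.2 names dispensing, collection and accounting records as examples of source documents.
- Section 10.2.1 lists accountability records among the contents of the site file.
- Section 11.2 has monitors confirm that product is accounted for as the law requires.

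None of these tells a site to keep capsules or narrows Section 6.9.

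**How does each case reach Section 6.9?**

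- Visit 8: directly, as an ATP visit with reconciliation.
- Early termination in the ATP: by a chain, from 5.4 and 7.2.8 to 7.2.5 to 6.9.
- Permanent stop with follow-up, such as pregnancy: not reached. No text says that reconciliation takes place at non-treatment visits, so the protocol is silent.

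**Is leftover drug expected?**

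Inputs: 0.5 mg/kg/day for 4 weeks, then 1.0 mg/kg/day for 16 weeks (Section 4.1); 30-day supplies at Visits 2, 4, 5, 6 and 7 (Sections 7.2.2 and 7.2.4); adherence threshold of 75% of doses (Section 6.9); weight 40 to 110 kg (Section 5.2.2).

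- Planned dose: 28 × 0.5 + 112 × 1.0 = 126 mg/kg over 140 days. This lies within the 120 to 150 mg/kg target of Section 6.1.
- Issued: 30 × 0.5 + 4 × 30 × 1.0 = 135 mg/kg over 150 days.
- Left at Day 140, full adherence: 150 − 140 = 10 supply-days; 135 − 126 = 9 mg/kg, which is 9 × 40 = 360 mg to 9 × 110 = 990 mg.
- Visit 8 window of ±4 days, with dosing up to the visit: 150 − 144 = 6 to 150 − 136 = 14 supply-days; 135 − 130 = 5 to 135 − 122 = 13 mg/kg. If dosing stops at Day 140 even when the visit is later, 9 mg/kg remains rather than 5.

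At 75% of doses, 0.25 × 140 = 35 days' doses are missed. The amount left depends on when:

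- All in the 1.0 mg/kg phase: 9 + 35 × 1.0 = 44 mg/kg.
- As many as possible (28) in the 0.5 mg/kg phase and 7 later: 9 + 28 × 0.5 + 7 × 1.0 = 30 mg/kg.
- Spread evenly over both phases: 135 − 0.75 × 126 = 40.5 mg/kg.

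Across the Visit 8 window the extremes are as follows:

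- Day 144, 36 days missed: 5 + 28 × 0.5 + 8 × 1.0 = 27 mg/kg.
- Day 136, 34 days missed, all at 1.0 mg/kg: 13 + 34 = 47 mg/kg.

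**How soon is the last test?** Visit 9 is nominally 168 − 140 = 28 days after Visit 8. With both windows the gap is 164 − 144 = 20 to 172 − 136 = 36 days.

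**How many might leave early?** Section 5.1 plans about 200 enrolled and about 140 completing the ATP, so about 60 would not complete it.

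**The case against.** The best defence is that Section 6.9 describes how adherence is measured, not what finally happens to the drug. On that view the sentence is a loosely drafted rule for mid-treatment visits. The mention of collection records in Section 10.1.2, the accountability provisions and the commitment to ICH-GCP (Section 12.1) all make it less likely that a site would hand capsules back at Visit 8. This is probably right about intent, and sites may well collect the drug in practice. It does not remove the point: the general provisions do not override a specific instruction that covers all unused drug.

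A second defence is that iPLEDGE binds females of childbearing potential and may deal with leftover capsules. The documents do not reproduce its rules on this, so it can be neither relied on nor dismissed.

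Third, harm needs someone to take capsules after treatment has ended, and the documents give no frequency for that. Retention also captures only what a subject brings in. Both limits stand, and they bear on how serious the gap is, not on whether it exists.

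A reader might also infer that the protocol directs sites to give a pregnant subject her capsules back. The text does not support that. Section 7.4.5 stops treatment and moves her to non-treatment or follow-up visits, and nothing links those visits to the return step.

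**Conclusion.** The point holds for Visit 8 directly and for early termination in the ATP through the cross-references. For a permanent stop with continued follow-up it is a gap of silence. It should be fixed. The wording most likely reflects a drafting oversight, and it would be wrong to infer that the sponsor deliberately sends drug home or that accountability is absent from the protocol.

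The most robust figure is a surplus of about 10 supply-days (about 9 mg/kg) at Visit 8 with full adherence. At 75% of doses it is about 30 to 44 mg/kg at Day 140, or about 27 to 47 mg/kg across the Visit 8 window. These figures assume a full 30-day supply at each of Visits 2 and 4 to 7, a change of dose at Day 28, no reduction for surplus already held, and exact weight-based dosing without capsule rounding. They also assume no dispensing at Visit 3. Table 1-1 and Section 6.3 suggest a supply there and Section 7.2.3 does not; if one is issued, more would remain. The textual gap does not depend on any of these amounts.

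**What to change.** Amend Section 6.9 so that capsules go back to the subject only at visits at which dosing continues. Add to Sections 7.2.5 and 7.2.8 that the site counts, retains and logs all unused capsules at Visit 8 and at early termination. Add to Section 6.9 that the same applies at the first visit after any permanent stop, and repeat this in Section 7.4.5 for pregnancy.

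The cost is a short wording change and minor storage, logging and disposal work. Visit 8 and early-termination visits already include reconciliation, so no new visit is needed there.
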